the use of HMG-CoA reductase inhibitors, multiple risk factors have been identified that independently correlate with atherosclerotic disease. Of these risk factors, the coronary artery calcium (CAC) score has emerged as a non-invasive independent risk factor for atherosclerotic disease and a tool for the prediction of future cardiac events in asymptomatic patients.² The CAC score has also been identified as having the ability to re-stratify³ and extend to multiple ethnic groups⁴ the predicted risk obtained from the Framingham risk score.

Although the role of the CAC score in the asymptomatic population has been well established its role in a symptomatic patient with suspected coronary artery disease is less clear.

Role of Calcium Scoring Prior to CCTA in the Symptomatic Patient

The most commonly utilized role of the CAC score prior to CCTA is as a gatekeeper to angiography because the specificity and accuracy of the CCTA may vary depending on the amount and location of the coronary calcium⁶. The decrease in sensitivity and specificity is often thought to be due to blooming artifact which can lead to an overestimation in the degree of stenosis or can make the segments un-interpretable on contrast CT angiography. Of note, the data from the Coronary Artery Evaluation Using 64-Row Multidetector Computed Tomography Angiography (CORE-64) study showed that the accuracy and negative predictive value of CCTA to detect a coronary stenosis $\geq 50\%$ in patients referred for ICA is reduced when the CAC score is ≥ 600 ⁷. In a meta-analysis by Abdulla, it suggests that careful pre-angiographic planning needs to occur in patients with CAC score ≥ 400 ⁸ to ensure appropriate study quality and diagnostic accuracy. Furthermore, multiple studies have revealed that high levels of coronary artery calcification is also one of the most important factors associated with a non-diagnostic coronary CTA^{9,10} leading an imager to decide to not proceed with angiography in cases of very high coronary calcification.

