Based on the above information, non-contrast CT scanning of the entire heart is usually performed in adults over 50-years of age in order to assess for the presence and severity of coronary artery calcium. This is performed so to identify patients with high degrees of coronary calcium such that the imagers may modify the scan parameters of the subsequent coronary CTA scan in order to optimize image quality and diagnostic accuracy of CCTA. Specific variables that may be adjusted on the subsequent CCTA scan based on the absence or presence and severity of CAC include: tube current (mA), tube potential (kV), use of high-definition scanning, and type of ECG gating/triggering. Of note, the performance of non-contrast CT scan prior to CCTA is typically done using the well-established Agatston method. In this method, the entire heart is scanned using a relatively high tube potential of 120 kV. While this higher tube potential may not be needed to identify calcium, it is a prerequisite in order to calculate an Agatston coronary artery calcium score and is therefore the standard method to perform non-contrast scanning prior to CCTA in our lab and most labs worldwide. Given that the prognostic value of CCTA is superior to calcium scoring, many wonder if the type of non-contrast scan should be modified in order to reduce patient radiation

exposure.

Importantly, it has been demonstrated that the majority of coronary artery calcification occurs in the proximal to mid portions of the coronary arteries¹³. This important fact suggests that a more focused field of view during scout non-contrast CT imaging prior to CCTA may be effective as scanning the entire heart while limiting radiation exposure.

Radiation Exposure

The Society of Cardiovascular Computed Tomography (SCCT) guidelines on radiation dose and dose-optimization strategies in cardiovascular CT states that the imager should attempt to limit the radiation dose to the lowest reasonable level while acquiring as much information as possible in the diagnosis and characterization of a patient's coronary artery disease.

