In patients randomized to undergo the modified non-contrast CT scan to assess coronary calcification burden, this study will be performed by a radiologist and cardiologist as follows: axial acquisition obtained at 70% of the R-R interval using the following parameters: rotation time 0.35 sec; collimation of 64 x 0.625mm; detector coverage of 20.0 mm; axial thickness 2.5; tube voltage 80kV and tube current 250mA. The scan length will be from 1 cm below the carina to the level beneath the proximal coronary vessels defined as the greatest diameter of the apex of the right atrium. This location has been chosen based off of the experience of the senior cardiologist and radiologist that by choosing this location you will be able to obtain the proximal portion of all the vessels to include the right coronary artery which can be the most difficult to image.

Following completion of the non-contrast CT, the clinically assigned radiologist and cardiologist will determine, based on the information from the non-contrast CT, whether to modify their initial CCTA acquisition parameters or if it is appropriate to continue with CT coronary angiography portion of the exam.

As per standard protocol, prior to initiating the coronary CT angiography, a clinical assessment with vital signs will be performed by a physician and sublingual nitroglycerin spray will be given to all patients for vasodilatation. A timing bolus technique (using 10 cc of iodinated contrast) will be used to determine appropriate timing of the contrast for CCTA, in typical fashion. Following the performance of the timing bolus, CCTA will be performed in accordance with the clinical cardiologist and radiologist parameters, in standard fashion using the injection of iodinated contrast material. The injection protocol will be in accordance with current CCTA lab protocols. Specifically, this will be performed by injecting a bolus of approximately 60 mL of iodinated contrast material (Isovue 370 or Visapaque 320 based on physicians discretion), followed by approximately 50 ml of a 50/50 contrast/saline mixture, then approximately 30 mL of saline solution injected into an antecubital vein via an 18-20 gauge intravenous catheter with an injection rate of 5mL/s by using a power injector.

All CCTA scans will be interpreted using 50% ASIR iterative reconstruction, as per standard CCTA lab protocol.

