projections. CCTA image quality will be assessed on a per-segment basis using the 18-segment SCCT model. Image quality will be assessed on a per-segment basis using the following 4-point scale:

Score 1: Non-diagnostic: Impaired image quality that precluded appropriate evaluation of the coronary arteries due to severe motion artifacts, extensive coronary calcifications, severe image noise, or insufficient contrast.

[figure not shown]
Score 2: Adequate: Reduced image quality because of artifacts due to motion, image noise or low contrast attenuation, but sufficient to rule out significant stenosis.

Score 3: Good: Presence of artifacts caused by motion, image noise, coronary calcifications or low contrast, but fully preserved ability to assess the presence of luminal stenosis as well as the presence of calcified and non-calcified coronary atherosclerotic plaque.

[figure not shown]
Score 4: Excellent: Complete absence of motion artifacts, strong attenuation of vessel lumen and clear delineation of vessel walls, with the ability to assess luminal stenosis as well as plaque characteristics.

The overall patient study quality will be determined by the mean of these scores after reaching consensus. In addition, CCTA signal (mean CT number, Hounsfield unit [HU]), noise (standard deviation in HU) and contrast/noise

The two readers will measure the signal and noise in the aortic root and each of the proximal coronary arteries with the mean of the readers used for comparisons. The contrast to noise will also be evaluated (difference of the mean arterial/aorta signal divided by the mean noise). *✓ this*

Flow sheet

5.5.1 Describe when, where and how the study subjects will be identified and recruited.

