5.7.1 Data Analysis Table

Aim 1- To assess the impact on CCTA image quality using modified calcium score approach.	
 - Image quality (4 point scale) - Signal/noise ratio 	
 - Treatment group - Treatment group 	
 - Two sample t-test or Mann-Whitney (dependent upon the distribution of the data). - Two sample t-test
Aim 2- To determine the rate of changes in the coronary CT angiography acquisition parameters of the modified versus standard calcium scoring	
 - Change in (increase or decrease) in tube current (mA) by 50 - Any change in tube potential (kV) - Change to/from retrospectively-gated CCTA - Any change in padding (acquisition window) - Changing to/from a high definition CT acquisition 	
 - Treatment group 	
 - Fisher's exact test

	All answered as yes/no		
Aim 3- To assess the difference in patient estimated effective radiation exposure (mSv) between the modified versus standard calcium scoring techniques.	- Average of radiation exposure (mSv)	- Treatment group	- Two sample t-test
Aim 4- To assess the difference in patient estimated effective radiation exposure (mSv) of the entire CCTA study (plus calcium scoring) between groups.	- Average of radiation exposure (mSv)	- Treatment group	- Two sample t-test

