5.8. Endpoints

Primary

The measurement of quality in comparison of the modified versus non-modified CCTA using a qualitative (four point scale and measure above) and quantitative (CCTA signal, noise, contrast to noise ratio) score.

Secondary

1. Any changes in the cardiac CT after evaluation of the modified or standard calcium scoring. These changes include: a change in mA by 50, any change in kV, any changes in padding and changing to high definition
2. The measurement of radiation exposure as DLP/milli-sieverts in comparison of the modified versus standard calcium scoring.
3. The measurement of radiation exposure difference measured as DLP/milli-sieverts of the entire CCTA study on the modified versus standard calcium scoring.
4. Whether the imager cancels the study based off of the modified or standard calcium scoring.

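### Signal, noise and contrast-to-noise share primary status with the 4-point quality score, yet a reassuring result on them would not by itself show that CCTA quality is preserved

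*Combined protocol and SAP*

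**What the plan says.** **Endpoint.** Section 5.8 names one primary endpoint with two parts, a "qualitative (four point scale and measure above) and quantitative (CCTA signal, noise, contrast to noise ratio) score". It does not say which part decides, or what follows if they disagree.

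**Measurement.** Section 5.5 (CCTA Interpretation and Review) states: "The two readers will measure the signal and noise in the aortic root and each of the proximal coronary arteries". Contrast to noise is the "difference of the mean arterial/aorta signal divided by the mean noise". The 4-point score is read on all 18 segments by two readers blinded to arm, with consensus. Scores 1 and 3 mention coronary calcification by name.

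**Analysis.** In the Aim 1 row of 5.7.1, the quantitative outcome is "Signal/noise ratio", compared by treatment group with a two-sample t-test. Section 5.7.2 gives a margin, SD and power for the 4-point score, and none for signal, noise or either ratio.

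**What calcium does and how imagers respond.** Section 4.1 attributes the loss of CCTA accuracy to "blooming artifact which can lead to an overestimation in the degree of stenosis or can make the segments un-interpretable". It says calcium lies mostly in the proximal to mid vessels and lists what imagers may adjust: "tube current (mA), tube potential (kV), use of high-definition scanning, and type of ECG gating/triggering". In 5.5 the lower limit of the modified scan is chosen so that "you will be able to obtain the proximal portion of all the vessels".

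**The concern.** The trial asks whether a shorter, lower-kV calcium scan lets CCTA quality slip. Section 6.2 acknowledges diminished accuracy as the possibility under study. The mechanism in 4.1 is local: a calcified segment blooms and becomes hard or impossible to read. Mean HU and its standard deviation in the aortic root and proximal coronaries are not designed to grade that, and they leave out the mid and distal segments.

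The readings also depend on settings the imager may change because of calcium. A difference between arms could then reflect a different choice of settings, and the absence of a difference could hide offsetting changes.

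Because 5.8 gives these measures equal primary standing, and 5.7.1 applies a difference test without a margin, a null or favourable result could be reported as primary evidence that quality is preserved. It would not support that conclusion.

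**Working it through.** **1. The plan's own figure for the 4-point score (5.7.2).** Inputs: means 3.20 and 3.15, SD 1.10, margin 0.49, 79 per group, one-sided alpha 0.05.
- Distance to margin: 0.49 − 0.05 = 0.44.
- Standard error: 1.10 × √(2/79) = 0.175.
- Power: Φ(0.44/0.175 − 1.645) = Φ(0.869) = 80.8%; by noncentral t, 80.5%.

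The stated 80% is reproduced. It belongs to the 4-point score alone.

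**2. What the signal/noise t-test can detect.** The documents give no SD, so I work in SD units, with 79 per group and two-sided 5%.
- 80% power needs a difference of 0.449 SD.
- Assume a share q of modified-arm patients shifts by 1 SD and the rest do not. The mean shift is q SD, with noncentrality q × √(79/2) = 6.285q.

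| q | mean shift (SD) | noncentrality | chance of significance in the true direction |
|---|---|---|---|
| 10% | 0.10 | 0.63 | 9% |
| 20% | 0.20 | 1.26 | 24% |
| 30% | 0.30 | 1.89 | 47% |

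If the loss lies wholly outside the measured sites and leaves these readings unchanged, the expected shift is 0 and the test rejects at its nominal 5%. In all these cases a non-significant result is the more likely outcome.

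**3. Does a setting change move the ratio in a known direction?** The documents do not say how each setting affects HU or noise, so everything in this step is assumed, for illustration.
- *mA raised by 50*, noise proportional to 1/√mA, base 300 to 600 mA: the ratio is multiplied by √(350/300) = 1.08 to √(650/600) = 1.04. It rises 4% to 8%.
- *kV from 100 to 120*, signal falling 20% to 25%, dose proportional to kV^2.5, noise to 1/√dose: noise factor (100/120)^1.25 = 0.796. The ratio is multiplied by 0.75/0.796 = 0.94 to 0.80/0.796 = 1.01.
- *High definition adding 10% to 30% noise*: multiplied by 1/1.3 = 0.77 to 1/1.1 = 0.91.

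If one arm made the kV change in 10 to 30 percentage points more patients, its mean ratio would move by at most 0.30 × (0.942 − 1) = −1.7% to 0.30 × (1.005 − 1) = +0.15%. The same excess of mA increases gives 0.10 × 4% = +0.4% to 0.30 × 8% = +2.4%. The two can cancel. Section 3 also counts mA decreases as changes. No net sign can be claimed.

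**4. The two parts of the endpoint side by side.**

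| | 4-point score | Signal, noise, contrast to noise |
|---|---|---|
| Sites | 18 segments | aortic root, proximal coronaries |
| Calcium in the definition | yes (Scores 1 and 3) | no |
| Margin and power | 0.49 points, 80% | none |
| Status in 5.8 | primary | primary |

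**The case against.** The best defence is that the other half of the endpoint already does the work. The blinded score grades calcification over all segments, and it carries the margin, the power, the kappa analysis and the ordinal regression. No text lets the quantitative measures decide the conclusion, and 5.7.1 states no favourable direction for the ratio. This stands, and it makes the point modest. It does not remove it, because 5.8 leaves both parts primary with no rule for reading them.

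A reader might infer two stronger things.

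- *That the quantitative measures cannot register calcium-related loss at all.* The documents do not support this. kV and mA apply to the acquisition, so an adjustment that was not made could appear as a change in noise at the measured sites. Proximal calcium inside a coronary region could also alter HU; the available text gives no placement rule for those regions. The 5.5 sentence introducing these measures breaks off, so the absence of further rules is uncertain.
- *That the measures are biased towards the modified scan.* This needs CT physics that the documents do not give, and mA increases push the ratio the other way. A calculation on mean HU alone would also miss the ratio that 5.7.1 tests. Section 5.7.2 assumes equal rates of any setting change (50% in each arm), so an imbalance is a departure from the planning scenario. Settings before and after the calcium scan are recorded (5.5.5) and changes are compared by arm, so an imbalance could be seen, though with limited power.

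The modified scan's lower limit is an axial level and does not exclude every mid segment. Mid and distal segments are therefore only an approximation to what it leaves uncovered.

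**Conclusion.** The point holds in a limited form and is a cheap improvement. Signal, noise and contrast to noise have unranked primary status, are read only in the root and proximal vessels, do not grade blooming or un-interpretable segments, respond to settings in a direction the documents leave open, and have no margin. A null or favourable result on them does not by itself show preserved CCTA quality. The blinded 4-point score can, if tested against its margin.

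This conclusion rests on the documents' text alone. The 9% to 47% range assumes a 1 SD shift in 10% to 30% of modified-arm patients, and the setting factors rest on outside physics; both are illustrations. No direction or size of bias is established.

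**What to change.** - In 5.8 and the Aim 1 row of 5.7.1, name the blinded consensus 4-point score as the single primary endpoint, tested for non-inferiority against the 0.49-point margin in 5.7.2.
- Make signal, noise and contrast to noise supportive, and state that they cannot alone support a conclusion of preserved quality.
- Add a supportive by-arm comparison of the segment scores for mid and distal segments, reported as an estimate with a confidence interval.
- Label any display by final kV or high-definition mode as descriptive. Both are settled after randomisation, so arm comparisons within those groups are not protected by it.

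The cost is wording in two sections and one tabulation of scores already collected, with no new patients or procedures. In exchange, the quantitative measures lose primary status, and the mid/distal comparison is unpowered and uses fewer segments per patient.

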5.5.2 Consent Process

- a. If eligible, the patient will fill out the 'Informed Consent Form and HIPAA authorization'. To prevent coercion the patient will be educated that enrollment is voluntary and his/her decision to participate will not impact our commitment to provide current standard of care. The patient must sign for himself/herself, no authorized legal representatives will be permitted to sign for the patient. The consent will take place in a clinic room in the cardiology clinic or in the prep and recovery area in the patient's personal bay to ensure privacy.
- b. Potential subjects will have as much time as needed to review the consent, ask the study Principal Investigator, study doctor, and/or site study coordinator questions about the consent and study, and will be reminded that they can at any time, if they are uncomfortable about participation, call the site study coordinator and/or the study PI to ask questions or withdraw.
- c. The investigators will request the subject voice an understanding of the consent form prior to signature and will prompt the subject for any questions prior to enrollment. A copy of the consent/HIPAA form with contact information for any questions will be provided to the patient at his/her request and the original copy will be kept in a secured location in the cardiology clinic to protect the patient's privacy.

5.5.3 Compensation for participation

N/A. No compensation will be given to patients for being in this study.

5.5.4 Research Interventions

No additional lab draws or nursing requirements are needed beyond current standard of care for the purposes of this research.

5.5.5 Data Collection

a. Method of Collection from Study Participants.

Data will be collected on data collection sheets prior to the patient's arrival, during the procedure and after the study has been performed.

Initial assessment will be collected according to the 'Patient Information' and 'CT Acquisition' Data Sheets to include the following information:

Patient Information Data Sheet:

- Age X Name
- Height/Weight
- Gender
- Ethnicity
- Cardiac risk factors
- Symptom status
- Reason for referral for CT coronary angiography
- Lab values (BUN, Cr, Total Cholesterol, LDL-C, HDL-C)
- Medications
- Prior stress testing
- Adverse Clinical Events
- Protocol Violations

'CT Acquisition Data Sheet':

- Date of scan
- Coronary calcium score
- CT acquisition premedication status
- Contrast (type, iodine concentration, volume)
- Type of scan (data acquisition): prospective ECG-triggered or retrospectively gated (pre and post calcium scoring)
- Padding (pre and post calcium scoring)
- Tube current (pre and post calcium scoring)
- Tube voltage (pre and post calcium scoring) High definition (Y/N)- please mark whether this was decided before or after calcium scoring
- Heart rate (pre/post scan)
- Dose length product
- Estimated mSv
- Adverse Events
- Protocol Violations

This information will be uploaded and encoded per patient by a unique, random identifier according

consent form to stay + source documents until study closes
with CRF ¹⁶ and redact PII

to procedures outlined in the study.

b. Source and Type of Data Collected from Existing Data Sources. Answer the questions below after considering the minimum necessary data required for the research study.

i. Have you received a data consultation with a data expert to determine the data elements to be extracted or the data system to access? (Consulting with a data expert often saves time later in the compliance process because the data expert can advise on the data available in the numerous MHS data systems, the quality of that data and the methods for encrypting and collapsing data. You may contact a data expert at the following email address: [contact])

Yes, then complete the questions in this subparagraph b according to the information received from the data consult

No, then complete the questions in this subparagraph b according to the best of your knowledge (NOTE: It is highly recommended to get a data consult.)

ii. Indicate whether you will receive a data extract from the MHS or will access a data system to create a data set. A data extract is when the MHS or a contractor provides the data set directly to the researcher. When receiving a data set through data extract, the researcher may indicate whether the data elements should be provided as is, encrypted or collapsed. In contrast to a data extract, access to a data system means that the researcher may access a data system and create a data set for the research study.

Data Extract Access

iii. Do you intend to use only a de-identified data set in your research study?

A de-identified data set is a data set that does not include any of the identifiers listed in the table in 5.5.5 (b)(vi). In addition, the researcher does not have actual

* knowledge of another way the data can be used alone or in combination with other known information to identify an individual. De-identified data is also data that a person, with appropriate knowledge of and experience with generally accepted statistical and scientific principles and methods for rendering information not individually identifiable, determines is not individually identifiable in accordance with the conditions outlined in 45 CFR 164.514 (b)(1).

Yes No

No

iv. Will you need MHS data with health information?

Data with health information means any information that is created or received by the MHS that relates to the past, present or future physical or mental health or condition of an individual, the provision of health care to an individual or the past, present or future payment for the provision of health care to an individual. Examples of MHS data with health information includes data maintained on AHLTA, CHCS and ESSENTRIS.

Yes No

v. Do you intend to access a data base to obtain personally identifiable information that is not health information (PII)?

Yes, will access data base for (PII)

No, will not access data base for PII

vi. Include the following table in your protocol and put an "x" in the MHS column next to the categories of data that you are requesting from the MHS. If you are planning to receive a data extract of MHS data that includes a data element that will be de-

identified by the MHS, then you do not need to put an "X" in the column corresponding to the category of data for that data element.

	Study Participant	MHS	Other
1. Names	X		
2. Postal address with only town, city, State and zip code			
3. All geographic subdivisions smaller than a State, including street address, city, county, precinct, zip code and their equivalent geocodes, except for the initial three digits of a zip code if, according to the current publicly available data from the Bureau of Census: 1) the geographic unit formed by combining all zip codes with the same three initial digits contains more than 20,000 people; and 2) the initial three digits of a zip code for all such geographic units containing 20,000 or fewer people is changed to 000.			
4. All elements of dates (except year) for dates directly related to an individual, including birth date, admission date, discharge date, date of death; and all ages over 89 and all elements of dates (including year) indicative of such age, except that such ages and elements may be aggregated into a single category of age 90 or older			
5. Telephone numbers			
6. Fax numbers			
7. Electronic mail addresses			
8. Social security numbers (In accordance with the DoD Social Security Number Reduction Plan, please justify the reason for collecting the social security number of study participants in the space after xi.)	X		
9. Medical record numbers			
10. Health plan beneficiary numbers			
11. Account numbers			
12. Certificate/license numbers			
13. Vehicle identifiers and serial numbers, including license plate numbers			
14. Device identifiers and serial numbers			

15. Web Universal Resource Locators (URLS)			
16. Internet Protocol (IP) address numbers			
17. Biometric identifiers, including finger and voice prints			
18. Full face photographic images and any comparable images			
19. Any other unique identifying number, characteristic, or code (DEERs ID, EDIPN, Rank)			

vii. If you are requesting access to an MHS data system, put an “x” in the Request from MHS column next to the MHS system(s) from which you are requesting data. If you do not know what system contains the elements you intend to request, please refer to the *Guide for DoD Researchers on Using MHS Data* or seek guidance from a data expert.

PHI Systems

MHS Data Systems	Request from MHS
AHLTA	X
CDM (from the MDR)	
CHCS	
ESSENTRIS	X
PDTS	
TRAC2ES	
M2	
MDR	
PDHRA	
PDHA	
TMDS	
PEPR	
JTTR	

PII Systems Only

MHS Data Systems	Request from MHS

DMDC	
MHS Learn	
DMHRSi	

De-Identified Data System

MHS Data Systems	Request from MHS
EAS	

Other Systems

List Other system(s):

viii. Do you intend to merge or otherwise associate requested data with data from any other sources outside of MHS, including other DoD sources that are not part of the MHS?

Yes, will merge data No, will not merge data

ix. Using the tables in 5.5.5 (b) (vi), put an “x” in the Other column next to the categories of data or data elements that include the data elements you intend to merge.

x. Is there any possibility that the data will become identifiable because of triangulation, a small cell size, or any unique data element(s)?

Triangulation means using different data elements that are not themselves identifiable but that in combination can be used to determine the identity of an individual. For example, triangulation would be using rank and race together to determine the identity of an individual with a particular health condition.

Small cell size means that the categories contain a small number of eligible individuals that satisfy the category description. Guidance for acceptable cell size is available from the Centers for Medicare and Medicaid Services. For example, the rank category of five star generals with a particular diagnosis may be less than 30 so the data category may need to include lower ranks too.

A unique data element includes any unique features that are not explicitly enumerated in the categories of data in Table vi above, but that could be used to identify an individual. Examples of unique data elements include 1) a unique number, such as a medical record number or EDIPN; 2) a unique code, such as a diagnosis code or a bar code on electronic health record; and 3) any unique characteristic, such as a high rank like general or admiral or a unique race or gender with another unique characteristic.

Yes, there is a reasonable possibility the data will become identifiable.

No, there is no reasonable possibility the data will become identifiable.

xi. Please justify the reason for collecting the social security number of study participants.

This data is obtained with all of our clinically indicated CCTAs to ensure that the correct study is performed on the correct patient. The social security number will not be included in the de-identified data associated with the patient.

